4E-BP1	Eukaryotic initiation factor 4E-binding protein 1
5-FU	5-fluorouracil
ACE	Angiotensin-converting enzyme
ADME	Absorption, distribution, metabolism, and excretion
AE	Adverse event
ALP	Alkaline phosphatase
ALT	Alanine aminotransferase
ANC	Absolute neutrophil count
AST	Aspartate aminotransferase
AUC	Area under the curve
β-hCG	β-human chorionic gonadotropin
BCS	Biopharmaceutics Classification System
BrdU	Bromodeoxyuridine
BUN	Blood urea nitrogen
CBC	Complete blood count
CDK	Cyclin-dependent kinase
CDKN2A	Cyclin-dependent kinase inhibitor 2A (gene)
CNS	Central nervous system
CR	Complete response
CRF	Case report form
CT	Computed tomography
ctDNA	Circulating tumor DNA
CYP	Cytochrome P450
DCR	Disease control rate
DLT	Dose-limiting toxicity
DNA	Deoxyribonucleic acid
DSMB	Data and safety monitoring review board
ECOG	Eastern Cooperative Oncology Group
ECG	Electrocardiogram
FOLFIRINOX	5-fluorouracil, irinotecan, oxaliplatin
GEM	Gemcitabine
GGT	Gamma-glutamyl transpeptidase
HIF-1	Hypoxia-inducible factor 1
HIV	Human immunodeficiency virus
HR	Hazard ratio
IHC	Immunohistochemistry
IND	Investigational new drug
INR	International normalized ratio
IV	Intravenously
LCCC	Lombardi Comprehensive Cancer Center
LD	Longest diameter
LFT	Liver profile
LLN	Lower limit of normal
MCL	Mantle cell lymphoma
MEF	Mouse embryonic fibroblast
MRI	Magnetic resonance imaging
mOS	Median overall survival
mPAC	Metastatic pancreatic adenocarcinoma
mPFS	Median progression-free survival
mTOR	Mammalian target of rapamycin
mTORC1	Mammalian target of rapamycin complex 1

NGS	Next-generation Sequencing
ORR	Overall response rate
OS	Overall survival
PCR	Polymerase chain reaction
PD	Progression of disease
PFS	Progression-free survival
PFS _{8 weeks}	Progression-free survival rate at 8 weeks
PgP	P-glycoprotein
PI	Principal investigator
PK	Pharmacokinetics
PO	By mouth
PR	Partial response
PS	Performance Status
PT	Prothrombin time
PTT	Partial thromboplastin time
QD	Once daily
RB	Retinoblastoma
RECIST	Response Evaluation Criteria in Solid Tumors
RNA	Ribonucleic acid
RP2D	Recommended Phase II Dose
RR	Response rate
S6K1	S6 ribosomal protein kinase
SAE	Significant adverse event
SD	Stable disease
SRS	Stereotactic radiosurgery
ULN	Upper limit of normal
VEGF	Vascular endothelial growth factor

STUDY SYNOPSIS

Title	A Phase I/II Study of LEE011 Plus Everolimus in Patients with Metastatic Pancreatic Adenocarcinoma Refractory to Chemotherapy
Short Title	LEE011 plus Everolimus in Refractory Pancreatic Cancer
Protocol Number	2016-0232
Clinicaltrials.gov number:	NCT02985125
Phase	Phase I/II
Investigational Agents	1) LEE011 (ribociclib), an oral CDK4/6 inhibitor (Novartis) 2) Everolimus (Afinitor®), an oral mTOR inhibitor (Novartis)
Indication	Metastatic pancreatic adenocarcinoma (mPAC) refractory to gemcitabine (GEM)- and 5-fluorouracil (5-FU)-based chemotherapy
Concept and Scientific Rationale	
Pancreatic adenocarcinoma has an overall poor prognosis, with an estimated five-year survival rate around 7.2%⁽¹⁾. Approximately 53% of patients have metastatic disease at diagnosis, and their prognosis is even more dismal with an estimated five-year survival rate around 2.3%⁽¹⁾. In the past, single-agent gemcitabine (GEM) was the preferred treatment option for advanced pancreatic cancer as it was shown to have a survival benefit compared to single-agent 5-FU, although the median progression-free survival (mPFS) was only 2.3 months compared to 0.9 months (P=0.0002)⁽²⁾.
 
The two largest first-line trials in metastatic pancreatic adenocarcinoma (mPAC) that demonstrated a survival benefit over single-agent GEM used FOLFIRINOX (oxaliplatin, irinotecan, leucovorin, and 5-FU)⁽³⁾ and GEM plus nab-paclitaxel⁽⁴⁾. Conroy et al. showed an improved disease control rate (DCR, the proportion of patients with a complete response (CR), partial response (PR), or stable disease (SD)) of 70.2% and mPFS of 6.4 months using FOLFIRINOX compared to 50.9% and 3.3 months using GEM (both P<0.001)⁽³⁾. Using nab-paclitaxel plus GEM, Von Hoff et al. also demonstrated an improved DCR (48% versus 33%, P<0.001) and mPFS, 5.5 versus 3.7 months (P<0.001), when compared to single-agent GEM⁽⁴⁾. Recently, we have seen patients who have had progression of disease on both lines of therapy and retain an adequate performance status for further treatment. Previous studies of third-line therapy in mPAC are limited but reveal stable disease in 25-31% of patients with no partial or complete responses (31% of patients in the GVAX/CRS-207 combination vaccine study had stable disease but only 52% of these patients were treated in the third-line setting)^(5, 6). Therefore, novel therapeutic options are needed both for pancreatic cancer in general as well as for this subset of patients with refractory mPAC.
 
We propose a therapeutic approach using agents that directly target the signaling pathways responsible for tumorigenesis. LEE011 (ribociclib, Novartis) is an oral small-molecule inhibitor of cyclin-dependent kinase 4 (CDK4) and cyclin-dependent kinase 6 (CDK6). CDK4/6 acts by phosphorylating and inactivating the retinoblastoma protein (RB), allowing E2F family transcription factors to accelerate cell cycle progression from G1 to S phase⁽⁷⁾. Pancreatic cancer is frequently associated with an alteration in the CDKN2A gene resulting in the loss of the p16INK4a protein that naturally inhibits CDK4/6⁽⁸⁾. LEE011 as a single agent has not


	
shown significant activity, likely due to aberrant induction of Cyclin D and E1⁽⁹⁾. The addition of an inhibitor of the mammalian target of rapamycin (mTOR) blocked this pathway and halted tumor cell proliferation when studied in pancreatic cancer cells xenograft models^(9, 10). The combination of everolimus (Afinitor®, Novartis), an mTOR inhibitor, with LEE011 is currently under evaluation in a Phase Ib/II clinical trial of LEE011, everolimus, and exemestane in patients with locally advanced or metastatic hormone-receptor positive, HER2-negative breast cancer (CLEE011X2106). We aim to study the combination of LEE011 and everolimus as third-line therapy in patients with mPAC refractory to 5-FU- and GEM-based chemotherapy.
 
Hypothesis: We hypothesize that the combination of LEE-011 and everolimus will improve the progression-free survival rate at 8 weeks from a historical baseline of 25% to a hypothesized rate of 50%.

Study Duration	24 – 29 months
Objectives	
Primary Objective of the Phase I Portion: To determine the Recommended Phase II dose (RP2D) of LEE011 in the combination with everolimus in patients with mPAC refractory to 5-FU- and GEM-based chemotherapy
 
Primary Objective of the Phase II Portion: To determine the progression-free survival (PFS) rate at 8 weeks (PFS_{8weeks}) to assess the clinical efficacy of the combination of LEE011 and everolimus in patients with mPAC refractory to 5-FU- and GEM-based chemotherapy
 
Secondary Objectives: To determine, in patients with refractory mPAC treat with LEE011 and everolimus:
 
 ▪ Median progression-free survival (mPFS) ▪ Median overall survival (mOS) ▪ Best overall response rate (ORR) ▪ Change in serum tumor markers (CA 19-9 or CEA) ▪ Safety and tolerability 
Exploratory Objectives:
 
 1) To correlate the PFS_{8weeks} to correlative scientific markers, including the analysis of tumor biopsies and blood-based markers, including RB, pRB, p16, cyclin D1, Ki67, MCM7, and pS6 levels by immunohistochemistry 2) To screen for use a targeted sequencing approach for genetic lesions observed in pancreatic cancer that includes KRAS, SMAD4, TP53, CDKN2A as well as other commonly mutated cancer genes. 3) To assess blood for the analysis of circulating tumor DNA as a surrogate marker of disease burden. KRAS and other mutations will be used as the determinants of tumor selective DNA
Number of Subjects	A minimum of 12 and a maximum of 44 evaluable patients
Diagnosis and Main Inclusion and Exclusion Criteria	
Key Inclusion Criteria
 
 1) Histologically confirmed metastatic adenocarcinoma of the pancreas with measurable disease per RECIST 1.1 2) Patient must consent to two mandatory biopsies and have tumor amenable to biopsy

	
- Tumor biopsies are mandatory UNLESS the patient has been evaluated for a biopsy in consultation with radiology in good faith, and there is a determination that an attempt at a biopsy would cause undue risk to the patient.
 
3) Documented progression of disease on at least one 5-FU-based regimen and at least one GEM-based regimen for metastatic disease (progression during or within 3 months of the completion of adjuvant therapy is acceptable)
 
4) Age \geq 18 years
 
5) ECOG performance status 0 or 1
 
6) Signed informed consent form
 
7) Adequate hepatic, bone marrow, and renal function as defined below in the body of the protocol
 
Key Exclusion Criteria
 
1) Patients previously exposed to, intolerant of, or ineligible for CDK inhibitors, mTOR inhibitors, and/or their combination
 
2) Prior anti-tumor therapy within 3 weeks of Cycle 1 Day 1 (anti-tumor therapy defined as, but is not limited to, anti-cancer agents (cytotoxic chemotherapy, immunotherapy, and biologic therapy), radiotherapy, and investigational agents), the “wash-out period”
 
3) Patients with known CNS metastases (that do not meet inclusion criteria, detailed below)
 
4) Active severe infection, or known chronic infection with HIV or hepatitis B virus
 
5) Cardiovascular disease problems including unstable angina, therapy for life-threatening ventricular arrhythmia, or myocardial infarction, stroke within the last 6 months, or a diagnosis of congestive heart failure
 
6) Patient has a concurrent malignancy or malignancy within 3 years prior to starting study drug, with the exception of adequately treated, basal or squamous cell carcinoma, non-melanomatous skin cancer or curatively resected cervical cancer.
 
7) Women who are pregnant or breastfeeding
 
8) Patient is currently receiving or has received systemic corticosteroids \leq 2 weeks prior to starting study drug, or who have not fully recovered from side effects of such treatment.

Study Design	
This study is a multi-institutional single-arm, open-label, Phase I/II trial of the combination of LEE011 and everolimus in refractory mPAC.
 
Phase I Portion
 
The Phase I portion of the study will be used to determine the R2PD for LEE011 for the Phase II portion of the study. Patients will be evaluated every 2 weeks for the first 8 weeks and then every 4 weeks thereafter. The dose of everolimus will remain constant at 2.5 mg by mouth daily every day, and LEE011 will be given daily days 1-21 out of a 28 day cycle with the dose determined by the patient cohort. A standard

3+3 design will be employed in which patients are enrolled in cohorts of 3 patients each (see figure 1):

- 3 patients are enrolled at dose level 1.
 - If 0 patients experience a DLT, 3 patients are enrolled at dose level 2.
 - If 1 patient experiences a DLT, 3 additional patients are enrolled at dose level 1. If 1 of 6 patients at dose level 1 experiences a DLT, 3 patients are enrolled at dose level 2.
 - If ≥ 2 patients experience a DLT, 3 patients are enrolled at dose level -1.
- If 0-1 of 3 patients at dose level 2 experience a DLT, then 3 additional patients are enrolled at dose level 2.
 - If 0-1 of 6 patients at dose level 2 experience a DLT, dose level 2 is the RP2D.
- If ≥ 2 of 3 patients at dose level 2 experience a DLT, 3 additional patients may be enrolled (to achieve 6 patients total) at dose level 1.
 - If 0-1 of 6 patients at dose level 1 experience a DLT, dose level 1 is the RP2D.
 - If ≥ 2 of 6 patients at dose level 1 experience a DLT, 3 patients are enrolled at dose level -1.
- If 0-1 of 3 patients at dose level -1 experience a DLT, 3 additional patients are enrolled at dose level -1.
 - If 0-1 of 6 patients at dose level -1 experience a DLT, dose level -1 is the RP2D.
 - If ≥ 2 of 3 or 6 patients at dose level -1 experience a DLT, 3 patients are enrolled at dose level -2.
- If 0-1 of 3 patients at dose level -2 experience a DLT, 3 additional patients are enrolled at dose level -2.
 - If 0-1 of 6 patients at dose level -2 experience a DLT, dose level -2 is the RP2D.
 - If ≥ 2 of 3 or 6 patients at dose level -2 experience a DLT, the study is terminated.

There will be no intra-patient dose escalation or de-escalation.

Patients enrolled in the Phase I portion of the trial who have received the recommended Phase II dose of LEE011 will be counted towards the Phase II efficacy analysis.

Table 1. Dose Escalation Schema

Dose Level	LEE011 (PO Days 1-21 out of a 28 Day Cycle)
2	300 mg
1	250 mg
-1	200 mg
-2	150 mg

[figure not shown]

Figure 1. Phase I Schema

Phase II Portion

Stage 1 – Initial Stage

The first stage of the Phase II portion of the study will be performed to establish a minimum level of clinical efficacy to warrant the enrollment of more patients in the second stage of the study. Using a Simon's Minimax two-stage design, 11 patients will be enrolled and will undergo baseline imaging and a pre-treatment biopsy. The patients will then be started on treatment with LEE011 at the RP2D by mouth daily for the first 21 days out of a 28 day cycle in combination with everolimus 2.5 mg by mouth daily continuously.

- **LEE011 at the RP2D by mouth once daily Days 1-21**
- **Everolimus 2.5 mg by mouth once daily Days 1-28 (continuously)**

Patients will be evaluated, including laboratory testing at screening, on Cycle 1 Day 1, and every 2 weeks until the first response assessment at 8 weeks, then every 4 weeks thereafter. Response assessment will occur every 8 weeks regardless of treatment cycle. If at the first response assessment there is no evidence of progression of disease (PD), as determined by RECIST v1.1 criteria, and the patient is tolerating therapy, then the patient may be seen only every 4 weeks, unless clinically indicated. Patients will continue to remain on study as long as there is no evidence of PD (according to RECIST v1.1 criteria) and the therapy is adequately tolerated.

Patients will have a tumor biopsy prior to treatment, a second biopsy at 2 weeks on treatment, and an optional final biopsy at the time of progression of disease (PD).

3.6.1.2 Stage 2 – Final Stage

After all 11 patients from the initial stage have undergone their 8 week response assessment, an interim analysis will be conducted to determine how many had a PR, CR, SD, or PD. The study will be stopped prematurely if 2 or fewer patients obtain a PR, CR, or SD at 8 weeks. If 3 or more patients obtain a PR, CR, or SD at 8 weeks, then 15 additional patients will be enrolled on the study for a total of 26 patients. Assuming a dropout rate of 10% in this refractory patient population, up to 3 additional patients may replace patients whose come off study prior to being evaluable for the primary endpoint (for reasons other than disease progression). Thus, up to 29 patients may be screened for the Phase II portion of this study.

	
Figure 2: Phase II Schema
 <pre> graph TD A[Patients enrolled N = 29] --> B[Pre-treatment biopsy and baseline imaging] A --> C[Drop out N ≈ 3] B --> D[LEE011 at RP2D by mouth daily 21/28 days plus everolimus 2.5 mg by mouth daily continuously] D --> E[Treatment biopsy after 2 weeks] D --> F[Interim futility analysis] E --> G[Response assessment every 8 weeks] G --> H[Continue treatment] G --> I[Progressive disease] H --> J[Treatment intolerability] J --> K[Final biopsy optional] I --> L[mPFS, mOS, ORR] K --> L </pre>

Multi-Institutional Trial Coordination
	
Personnel At each site, personnel dedicated to this protocol will be:
 
 - A site PI - A research coordinator/data manager 
In addition, at Lombardi-Georgetown, there will be a dedicated “multi-institutional” research coordinator who will play the primary role in coordinating the trial between Lombardi-Georgetown and additional sites. This coordinator will be the main point of contact for [name] and the other site PIs for any study related concerns, and to screen each patient being considered for enrollment (Including “remote” screening for the patients being screened at other sites). This coordinator will also be the point of contact for the data managers for data entry questions. Finally, this coordinator will play a major role in regulatory coordination of the study, specifically by: 1) reviewing and confirming all study-related adverse events; 2) submitting all SAE reports to the Georgetown IRB; and (the research coordinators at the other sites will prepare SAE reports for patients treated at their respective sites, but the “multi-institutional” coordinator will submit the final report); 3) gathering and preparing all primary source data for review/audit.
 
Patient Enrollment Enrollment at the sites will be competitive. If a patient is being screened for enrollment, the local research coordinator must send a secure/encrypted email within 24 hours containing the patient’s name, to the local PI, to [name], and to the multi-institutional coordinator. If a patient is successfully screened, the local research coordinator must send all supporting documentation to the multi-institutional research coordinator (by email or fax). Patients should not start therapy until both [name] and the multi-institutional coordinator have reviewed the patient’s records and confirmed that the patient is indeed eligible for enrollment.
 
Data Collection and Management Patient data will be entered into the online accessible database. This database is housed at Lombardi-Georgetown, but is accessible anywhere there is Internet access. The data manager and research coordinator at each site will attend an online training session so that they may learn how to enroll data into the database. All screening data should be entered prior to starting therapy, and all ongoing patient data should be entered within one week of each patient visit.
 
Conference Calls A monthly conference call will be held between Lombardi-Georgetown and the other sites meeting will be held to review patient enrollment, toxicity, and response assessment.


	
Trial Auditing
 
The multi-institutional coordinator will arrange all primary source documents for the patients to be audited. This will include collecting copies of the primary source data for any patients treated at other sites.

Statistical Design, Feasibility, and Trial Duration
	
This is a multi-institutional single arm, open label Phase I/II study to evaluate the PFS_{8weeks} of the combination of LEE-011 plus everolimus, in patients with metastatic pancreatic cancer refractory to 5-fluorouracil (5-FU) and gemcitabine-based chemotherapy. Previous studies of third-line therapy in mPAC are limited but reveal stable disease in 25-31% of patients with no partial or complete responses (31% of patients in the GVAX/CRS-207 combination vaccine study had stable disease but only 52% of these patients were treated in the third-line setting)^(5, 6). It is hoped that the combination of LEE-011 plus everolimus can increase the PFS_{8weeks} to at least 50%, though early stopping rules are in place for lack of efficacy.
 
All patients meeting the eligibility criteria and who have signed a consent form, have begun treatment, are not lost to follow-up, and are not taken off study for reasons other than progression or death before 8 weeks will be considered evaluable for the assessment of the DCR.
 
Between 12 and 24 patients will be enrolled in the Phase I portion of the study, depending on whether DLTs occur and dose de-escalation is required. The 6 patients treated at the RP2D will be included in the Phase II portion of the study. We anticipate the combination will be well tolerated such that all of the patients in the Phase I portion are likely to be evaluable for the Phase II efficacy analysis.
 
26 evaluable patients will be enrolled in the Phase II portion of the study (though the potential drop-out rate is 10%), which will provide a 90% power to detect an improvement in the DCR from 25% (based on historical control) to 50%, assuming a 1-sided significance level of 0.1 and an accrual rate of 2 patients per month. A Simon's optimal two-stage design will be used to test the null hypothesis that the DCR $P \leq 0.25$ versus the alternative that $P > 0.5$. For the first stage, 11 patients will be entered to the study. The trial will be terminated if 2 or fewer patients achieve a PR, CR, or SD at 8 weeks. If at least 3 patients in the first stage achieve a PR, CR, or SD at 8 weeks, the trial goes on to the second stage. A total of 26 patients will be enrolled. If the total number of patients who achieve a PR, CR, or SD at 8 weeks is less than or equal to 9, the combination therapy will be rejected. If however, 10 or more patients achieve a PR, CR, or SD at 8 weeks the combination therapy will be considered for further analysis.
 
With 26 evaluable patients in the Phase II portion, combined with a minimum of 12 to a maximum of 18 patients enrolled strictly in the Phase I portion of the trial, there will be up to 44 patients enrolled. At an expected accrual rate of 3 patients per month, the expected accrual duration will be approximately 15 months.
 
Descriptive statistics will be used to summarize patients' demographics, toxicity, and quality of life. The PFS_{8weeks} will be estimated from the observed data with 95% exact binomial confidence interval. The nonparametric Kaplan-Meier method will be used to estimate the survival function and calculate the PFS and OS. The ORR will be estimated from the observed data with 95% exact binomial confidence intervals.

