4.1.2 Phase II Portion, Stage 1 – Initial Stage

The first stage of the study will be performed to establish a minimum level of clinical efficacy to warrant the enrollment of more patients in the second stage of the study. 11 patients will be enrolled and will undergo baseline imaging and a pre-treatment biopsy. The patients will then be started on treatment with at the RP2D by mouth daily for the first 21 days out of a 28 day cycle in combination with everolimus 2.5 mg by mouth daily continuously.

- LEE011 at the RP2D by mouth once daily days 1-21

- Everolimus 2.5 mg by mouth once daily days 1-28 (continuously)

Patients will be evaluated, including laboratory testing, every 2 weeks until the first restaging analysis. Restaging will occur every 8 weeks regardless of treatment cycle. If at first restaging there is no evidence of PD, as determined by RECIST v1.1 criteria, and the patient is tolerating therapy, then patients may be seen only on Day 1 of future cycles, unless clinically indicated.

Patients will have a tumor biopsy prior to treatment, a second biopsy at 2 weeks on treatment, and an optional final biopsy at the time of PD.

After all 11 patients from the initial stage have undergone their 8 week response assessment, an interim analysis will be conducted to determine how many had a PR, CR, SD, or PD. The study will be stopped early if 2 or fewer patients obtain a PR, CR, or SD at 8 weeks. If 3 or more patients obtain a PR, CR, or SD at 8 weeks, then 15 additional patients will be enrolled on the study for a total of 26 patients. Up to 3 additional patients may be screened and may be used to replace up to 3 patients in the initial 26 patients, provided those initial patients undergo screening but do not start study treatment within 3 weeks of screening. Thus, up to 29 patients may be screened for the Phase II portion of this study.

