7.3 Evaluation of Best Overall Response

The best overall response is the best response recorded from the start of the treatment until disease progression/recurrence (taking as reference for progressive disease the smallest measurements recorded since the treatment started). The patient's best response assignment will depend on the achievement of both measurement and confirmation criteria.

Table 12. Response Evaluation. Note: If subjects respond to treatment and are able to have their disease resected, the patient's response will be assessed prior to the surgery.

Target Lesions	Non-Target Lesions	New Lesions	Overall Response	Best Response for this Category Also Requires:
CR	CR	No	CR	>4 wks. confirmation
CR	Non-CR/Non-PD	No	PR	>4 wks. confirmation
PR	Non-PD	No	PR	
SD	Non-PD	No	SD	Documented at least once >4 wks. from baseline
PD	Any	Yes or No	PD	no prior SD, PR or CR
Any	PD*	Yes or No	PD	
Any	Any	Yes	PD	

* In exceptional circumstances, unequivocal progression in non-target lesions may be accepted as disease progression.

Note: Patients with a global deterioration of health status requiring discontinuation of treatment without objective evidence of disease progression at that time should be reported as "symptomatic deterioration". Every effort should be made to document the objective progression even after discontinuation of treatment.

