9.3 Sample Size Considerations

Using a Simon Minimax 2-stage design with a null hypothesis of 25% and an alternative hypothesis of 50% (or greater) a total of 26 evaluable patients are needed (assuming 90% power and $\alpha=0.1$ (one-sided)).

For the Phase I portion, there may be as few as 12, and as many as 18 patients enrolled strictly in the Phase I portion (and not treated at the RP2D of LEE011, thus not counted towards the Phase II portion of the study). Thus, as many as 44 patients may be accrued for this trial. Anticipating an accrual rate of 3 patients per month, the trial is expected to complete accrual in approximately 15 months.

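### The synopsis replaces treated patients who leave before week 8 and the body does not; following the synopsis can raise type I error from 0.086 to about 0.14 at 10% drop-out if all leavers are failures

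*Combined protocol and SAP*

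**What the plan says.** - **Evaluable set.** The synopsis (Statistical Design, Feasibility, and Trial Duration) limits the set to eligible, consented patients who started therapy and remained in follow-up. It also requires that patients "are not taken off study for reasons other than progression or death before 8 weeks will be considered evaluable". The sentence is written for the disease control rate, but the event tested there (CR, PR or SD at 8 weeks) is the primary endpoint of section 9.4.1.
- **Replacement, synopsis** (Study Design, Stage 2 – Final Stage). Allowing for 10% drop-out, "up to 3 additional patients may replace patients whose come off study prior to being evaluable for the primary endpoint"; exits due to progression do not qualify. At most 29 patients may be screened.
- **Replacement, body.** Section 4.1.2 also allows 3 replacements, but "provided those initial patients undergo screening but do not start study treatment within 3 weeks of screening". Section 9.2 has the same condition.
- **Size and rule.** Section 9.3 states that "a total of 26 evaluable patients are needed"; section 9 does not define evaluable. At stage 1, with 11 patients, "The trial will be terminated if 2 or fewer patients achieve a PR, CR, or SD at 8 weeks". Section 9.5.1 declares success at 10 or more.
- **Patients with no 8-week scan.** Section 9.4.1 makes success a CR, PR or SD on imaging at the 8-week assessment. Section 2.4 makes the endpoint positive when there is no evidence of progression at 8 weeks. Neither says how to code a patient who was not scanned.

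**The concern.** The plan has two incompatible rules for who fills the 26 places in its go/no-go test. Under the synopsis rule, a treated patient who stops early for toxicity, withdrawal or investigator decision can be taken out and another treated patient put in. Such exits may well be linked to poor outcome: Table 11 takes patients off study for toxicity, and section 4.4.9.1 removes them for clinical deterioration. Under section 9.4.1 a patient with no 8-week CR, PR or SD cannot be a success, so each replacement exchanges a non-success for a new chance of success. In a single-arm trial judged against a fixed 25%, this affects both the futility look and the final decision. No analysis of all treated patients is planned that would show the effect.

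**Working it through.** **Inputs from the documents.** Null 25%, alternative 50%; "assuming a 1-sided significance level of 0.1"; "90% power to detect an improvement in the DCR from 25% (based on historical control) to 50" percent; stop at 2 or fewer of 11; success at 10 or more of 26; 10% drop-out; at most 3 replacements.

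**Inputs assumed.** Drop-out d of 5 to 20%. The success rate of leavers relative to all treated patients, f, is not in the documents; I take 0, 0.5 and 1.

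**1. The plan's own figures.** With b the binomial probability,

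P(success) = Σ (x = 3 to 11) b(x; 11, p) × P[Bin(15, p) ≥ 10 − x].

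At p = 0.25 this is 0.0857 and at p = 0.50 it is 0.9005, so the stated 0.10 and 90% are reproduced. Also 26/(1 − 0.10) = 28.9, which rounds up to the stated 29.

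**2. Exclusion without replacement.** The rule is a count. A leaver who is dropped and not replaced adds no success, exactly as a counted failure does. If all leavers are failures, each treated patient still adds a success with probability 0.25, so type I error stays at 0.0857 for every d. The estimate does move: at d = 10% the expected evaluable rate is 0.25/0.90 = 27.8% when the all-treated rate is 25%.

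**3. Synopsis rule, at most 3 replacements.** Fill 26 places in order, 11 and then 15. Each treated patient leaves with probability d. The first 3 leavers are replaced by newly treated patients; later leavers keep their place and add no success. A patient who stays succeeds with probability q = 0.25(1 − d·f)/(1 − d), which keeps the all-treated rate at 25%. Summing exactly over successes and replacements used, with the stage 1 stop, gives these type I errors:

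| Drop-out d | q if f = 0 | Leavers all fail (f = 0) | Leavers succeed half as often (f = 0.5) |
|---|---|---|---|
| 5% | 26.3% | 0.112 | 0.098 |
| 10% | 27.8% | 0.136 | 0.103 |
| 15% | 29.4% | 0.150 | 0.100 |
| 20% | 31.3% | 0.158 | 0.091 |

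If leaving is unrelated to outcome (f = 1), q = 0.25 and the error does not exceed 0.0857.

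**4. Upper bound.** At most 29 patients are treated, and success needs 10 successes among them. Even without the futility stop, P[Bin(29, 0.25) ≥ 10] = 0.166.

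**5. What a bare pass means.** 10/26 = 38.5%. If 3 treated patients were replaced and had no success, the same result is 10/29 = 34.5% of those treated.

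**6. Counting all treated patients.** With 26 treated and leavers counted as failures, type I error is 0.0857 at an all-treated rate of 25%, and power is 0.9005 if 50% is an all-treated rate. If 50% was meant for evaluable patients, the all-treated rate at 10% drop-out is 0.50 × 0.90 = 45%, and P(success) at 0.45 is 0.786.

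**The case against.** The strongest reply is that the body of the protocol already has a sound rule: under sections 4.1.2 and 9.2 no treated patient is replaced and the go/no-go error is intact. That is right. The inflation comes only from following the synopsis sentence, but the document does not say which text governs.

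Second, a reader might infer the error by putting 0.25/(1 − d) straight into the two-stage formula, which gives 0.151, 0.199 and 0.262 at 10, 15 and 20% drop-out. The documents do not support these figures. They need unlimited replacement, while the synopsis caps it at 3, and the last two exceed the bound of 0.166. For the same reason, exclusion by itself cannot be said to break the error rate.

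Third, a reader might infer that everyone who deteriorates drops out of the denominator, because section 7.3 has a category for "Patients with a global deterioration of health status requiring discontinuation of treatment without objective evidence of disease progression". Sections 7.4 and 4.4.9.1 recognise clinical progression, and the synopsis keeps progression and death evaluable, so many such patients can remain as failures. Those excluded would then be mainly patients who leave for toxicity, withdraw or are lost to follow-up. The documents give no outcome for them, so f = 0 is a worst case and not a finding.

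Finally, the documents do not say how the historical 25% treated non-evaluable patients. If it was an evaluable-only rate, an evaluable-only comparison would be like for like. This stands as an uncertainty, but it does not settle which replacement rule applies.

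**Conclusion.** The point holds as a contradiction in the replacement rule, together with an evaluable set that section 9 uses but does not define. That much needs no assumption. The size does: given an all-treated rate of 25% and the synopsis cap, the plan's own 10% drop-out gives a type I error of about 0.14 against the stated 0.10 if every leaver is a failure, about 0.10 if leavers succeed half as often, and no inflation if leaving is unrelated to outcome. The wording should be settled before the 11-patient look, because the same set decides the futility stop and the final conclusion. The gap between sections 2.4 and 9.4.1 belongs to the same correction: read literally, section 2.4 could code an unscanned patient as progression-free.

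**What to change.** 1. Use one replacement rule throughout, that of sections 4.1.2 and 9.2 (never-treated patients only), and delete the synopsis sentence on replacing patients who come off study.
2. In section 9 and the synopsis, define the primary set as all eligible patients who receive at least one dose at the RP2D.
3. Count anyone without documented CR, PR or SD at the 8-week assessment as a failure, at both stages, and align section 2.4 with section 9.4.1.
4. Keep 26 treated patients and the existing cut-offs (stop at 2 or fewer of 11; success at 10 or more of 26). The 10/26 cut-off must not be carried over to 29 treated patients: at least 10 of 29 after the same stage 1 gives a type I error of 0.148, while at least 11 of 29 gives 0.080 with power 0.914.
5. Report the evaluable-only rate as a sensitivity analysis.

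The cost is wording; the sample size does not change. The observed rate may be lower. If the 50% target was meant for evaluable patients, power at 10% drop-out is about 79%, and the protocol should say so.
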